We propose a prospective, double-blinded randomized controlled study of the efficacy of tranexamic acid in patients undergoing reduction mammoplasty. Our primary outcome variable will be rate of hematoma development. Our secondary outcome variables will be rate of blood transfusion, incidence of deep venous thrombosis, and rate of thromboembolic events. We will also collect a broad range of preoperative variables, surgical details, and other characteristics that may impact the perioperative bleeding risk. We hope to contribute to the growing body of literature supporting tranexamic acid to reduce unwanted surgical bleeding. Given the paradigm shifts evidenced by the recent surge in interest regarding tranexamic acid across multiple surgical subspecialties, better

understanding of the efficacy of tranexamic acid in plastic surgery may have powerful implications for surgical outcomes in our field.

2) Significance

The current proposal builds logically upon the prior research at our institution, which has been conducted by the PI and the Co-Investigator ([name]). We have sought to identify risk factors for hematoma development following reduction mammoplasty in our patient population, which has higher rates of obesity, hypertension, and diabetes compared to the national average. We have identified a hematoma rate of 7% in our patient population per a retrospective chart review, which is consistent with the prior literature. The PI's research focuses on optimizing surgical outcomes in breast-related procedures, providing a strong and pertinent research background for the proposal.

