There is a large body of evidence supporting the use of tranexamic acid to reduce perioperative blood loss and need for transfusion in trauma, orthopedic, and cardiac surgery.⁷⁻¹¹ Within the field of plastic surgery, previous research has focused on craniomaxillofacial surgery, though there have been preliminary studies of tranexamic acid's utility in burn surgery and aesthetic surgery.^{6,13} Though virtually all authors endorse the integration of tranexamic acid into clinical practice based on their findings, there have been few adequately powered randomized studies in plastic surgery.^{14,15} Furthermore, the majority of prior studies utilized primary outcome variables of unclear clinical significance. In a 2015 randomized controlled trial of 30 patients undergoing reduction mammoplasty, Ausen *et al* described an average 10 cc decrease in 24-hour drain output from topical TXA-treated breasts compared to contralateral controls, which was found to be statistically significant, but otherwise with uncertain clinical implications.¹⁶ In their discussion, Ausen *et al* write that their study was inadequately powered to determine whether or not tranexamic acid could prevent postoperative hematoma.

This study would be the first randomized controlled trial to evaluate the use of tranexamic acid in reducing the rate of hematoma development in patients undergoing reduction mammoplasty. We plan to expand on the findings of Ausen *et al* by selecting hematoma development as the primary outcome variable. Selecting reduction mammoplasty patients as the study population allows us to evaluate each patient as their own internal control, thereby eliminating potential confounders associated with an increased risk of hematoma, such as hypertension.¹⁴ Moreover, breast procedures have been identified as an independent risk factor for hematoma development compared to trunk, extremity, or facial plastic surgery procedures.³ With the large volume of body contouring surgery at our institution, as well as the higher rates of medical comorbidities associated with hematoma formation present in our patient population, we are uniquely equipped to conduct this study. This innovative study will provide high-level evidence regarding the use of tranexamic acid in plastic surgery in an elegant model.

3) Study Design

a) Study Objectives

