The primary goal of this proposal is to determine the efficacy of tranexamic acid in reducing the rate of hematoma formation after breast reduction surgery. This will be a double-blinded, randomized controlled study. The research will be achieved by randomizing one breast in a bilateral breast reduction to receive topical tranexamic acid, while the other breast will not receive the study drug. Both the surgical team and the patient will be blinded to which side has received the study drug. The patient will then be followed for the standard postoperative period and the rate of hematoma development will be recorded. Patient demographics, comorbidities, treatment history, and surgical details will be collected from these charts and analyzed for their impact on perioperative blood loss. **We hypothesize that use of topical tranexamic acid will decrease the rate of hematoma formation and the rate of blood transfusion without increasing the incidence of deep vein thrombosis or thromboembolic events.**

b) Target Population and Recruitment Methods

Consecutive patients presenting for breast reduction mammoplasty performed by plastic surgeons affiliated with Montefiore Medical Center will be offered enrollment in the study. Potential study participants will be recruited at their preoperative consultation appointments that take place at the Hutchinson Metro Center campus. Written informed consent (detailed below) will be obtained from all participants before inclusion. As this proposal involves greater than minimal risk to patients, we will have a Data and Safety Monitoring Plan in place prior to beginning the study.

c) Inclusion and Exclusion Criteria

Inclusion criteria include: being over the age of 18 and being scheduled for reduction mammoplasty at the Hutchinson Metro Center campus of Montefiore Medical Center.

Exclusion criteria include: oncologic breast reductions, unilateral breast reductions, history of thromboembolic disease, history of bleeding diatheses, history of stroke, current pregnancy, severe comorbidity (defined as American Society of Anesthesiologists (ASA) fitness grade IV or above).

d) Primary and Secondary Outcomes

Primary outcome: development of hematoma within 30 days of surgery

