Subject treatment assignments will remain blinded until the final subject has completed follow up and all data has been recorded and validated. Urgent, immediate unblinding due to medical emergency may be authorized by the Investigator. When possible, the treatment assignment will be provided to the treating physician in order to maintain the blind for the Investigator and study staff.

8. Data Analysis

We hypothesize that use of topical tranexamic acid will decrease total perioperative blood loss, hematoma formation, and transfusion rates without increasing the incidence of deep vein thrombosis or thromboembolic events.

a) Chart review data:

Patient charts will be abstracted for baseline demographic data and medical comorbidities that may independently increase the risk of developing a postoperative hematoma. Data to be abstracted from the medical record includes: demographic data (including patient gender, age, ethnicity), medical data (including body mass index, comorbidities (e.g. hypertension, diabetes, hyperlipidemia, coronary artery disease), smoking history, history of neoadjuvant radiation therapy or chemotherapy, history of thromboembolic disease, bleeding diatheses, or use of anticoagulant medications), surgical data (including type of operation performed, surgical team involved, weights of tissue removed, estimated blood loss, drain outputs in the immediate postoperative period, date that drain(s) were removed) and complications within 30 days of the index operation including hematoma requiring operative washout or bedside evacuation, seroma, cellulitis, nipple-areolar complex necrosis, fat necrosis, delayed wound healing, deep vein thrombosis and pulmonary embolism. Patients with insufficient records or those who are lost to follow-up will be excluded from the final analysis.

b) Statistical Analysis

[figure not shown]
We have partnered with our institution's Department of Surgery faculty biostatisticians on the statistical methods for this proposal. **Based on a Bayesian approach, a sample size of 100 patients will be sufficient to adequately power this study.**

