The primary objective of this pilot study is to explore whether, and to what extent, treatment using TXA decreases the risk of hematoma in patients undergoing breast reduction mammoplasty (BRM) compared to a saline placebo. A double-blind within-subjects design will be used with each patient receiving both treatments and thus serving as their own control. A simple randomization scheme will determine which treatment will be used for each side (left or right) for each patient. A Bayesian approach will be employed to estimate the posterior probability distribution of the

relative risk reduction in post-surgical hematoma between treatment rate between treatment with TXA and control. This posterior probability distribution provides the information necessary to answer the salient questions informative about the presence and strength of an efficacy signal for TXA; specifically, what is the probability that treatment with TXA reduces the risk of hematoma, compared to control by an amount δ for any $0 < \delta < 1$. Note that the probability that the relative risk < 1 corresponds to the probability that treatment with TXA is superior to the control. A description of this approach follows.

Prior to data collection and consistent with a null hypothesis of no difference between treatments we assume that the effect of treatment with TXA is equal to the effect of treatment with control. This assumption is formalized by assuming that the probability of developing a hematoma is the same for each treatment. The Bayesian approach considers this prior probability of developing a hematoma to be a random variable, which we specify to be a beta distribution with parameters 0.35 and 4.65, translating into a mean of 0.07 (the assumed hematoma rate for both treatments under the “null” hypothesis) and a standard deviation of about 0.10. Since patients will be treated with both treatments, the prior probabilities of developing a hematoma are not assumed to be independent. In our approach, we assume a conservative correlation of 0.30.

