This prior probability is combined with the observed data, the number of observed hematomas under each treatment (a binomial random variable) to yield an estimated posterior probability distribution for each hematoma rate. These estimated rates will be used to estimate the posterior distribution for the relative risk, and its natural logarithm which has the advantage of being approximately normally distributed and less skewed given the low expected hematoma rates.

An illustration of the estimated probability distribution for the natural logarithm of the relative risk is shown (left) under the “alternative” hypothesis that treatment with TXA reduces the rate of hematoma by a relative 50% compared to control based on a sample of 100 patients, the proposed sample size. The distribution is obtained by simulation using 100,000 replications. The sample size of 100 was chosen to ensure a high probability of detecting an efficacy signal (a relative risk of 0.5 or less) should it exist.

Specifically, with a sample size of 100, the probability of estimating a relative risk < 1 , or natural logarithm of the relative risk < 0 (i.e., estimating that treatment with TXA is superior to treatment with control) is approximately 80%, corresponding to an odds of 4:1. This 80% probability corresponds to the frequentist notion of power.

Note that the prior odds (assuming equal rates of hematoma) of observing a relative risk less than one is 1:1. Also, the probability of observing odds of 4:1 in favor of TXA under the assumption of equal hematoma rates using each treatment is approximately 20%. This 20% is a false positive rate corresponding to the frequentist Type I error rate.

We will perform a corresponding frequentist analysis using conditional logistic regression to estimate the odds ratio and corresponding 95% confidence interval for developing a hematoma using TXA compared to control. Our use of a non-informative prior ensures that these results will be consistent with those provided by the Bayesian approach, and thus enhance interpretation of the trial's results. Descriptive statistics, using both numerical and graphical summaries, will be used to describe the sample with respect to demographics, baseline characteristics, and important outcomes.

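### The objectives and sample-size text claim more than a self-described pilot can show, and the supplementary 95% interval has no stated precision and fails in the results most favourable to TXA

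*Combined protocol and SAP*

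**What the plan says.** All references are to the combined protocol and SAP.

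- Section 3 a), Study Objectives: "The primary goal of this proposal is to determine the efficacy of tranexamic acid in reducing the rate of hematoma formation". This sentence carries no qualifier.
- Section 8 b), Statistical Analysis, opening: "a sample size of 100 patients will be sufficient to adequately power this study". The sentence begins by tying the claim to a Bayesian approach.
- Section 8 b), next paragraph: "The primary objective of this pilot study is to explore whether, and to what extent" TXA lowers the risk of hematoma.
- Section 8 b), later: with 100 patients and a halved rate, the probability of estimating a relative risk below 1 is put at about 80% and likened to power. The chance of reaching 4:1 odds for TXA when the rates are equal is put at about 20% and likened to type I error.
- Section 8 b), supplementary analysis of the primary endpoint: "using conditional logistic regression to estimate the odds ratio and corresponding 95% confidence interval for developing a hematoma". The text expects it to agree with the Bayesian result and to help interpretation. It states no power, expected width or interval type.

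**The concern.** A trial meant to settle efficacy and a pilot meant to look for a signal license different conclusions, and the plan does not say which one governs the report. The only analysis with a stated 95% level rests on very few patients.

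Two misreadings follow if the stronger wording stands. An interval that includes 1, which is the likely result even if TXA halves hematomas, could be reported as a negative finding from an adequately powered trial. A favourable posterior, reached under a rule with a declared 20% false positive rate, could be reported as established efficacy.

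There is also a practical defect. The standard conditional logistic interval does not exist when no patient has a hematoma on the TXA side only, which is the pattern that most favours TXA.

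**Working it through.** **Inputs.** n = 100 pairs (section 8 b). Control rate p1 = 0.07: "translating into a mean of 0.07 (the assumed hematoma rate for both treatments under the" null hypothesis, read here as a rate per breast. TXA rate p2 = 0.035, from the plan's relative 50% reduction. The plan's 0.30 is a correlation between prior probabilities. It gives no within-patient correlation of outcomes, so ρ = 0 to 0.30 is an assumption.

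**The plan's own figures.** With independent Beta(0.35 + x, 4.65 + 100 − x) posteriors averaged over simulated trials:

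- The mean posterior probability that RR < 1 is 78.9% (ρ = 0) or 80.9% (ρ = 0.30) when TXA halves the rate. This reproduces the 80%.
- Under equal rates, that probability reaches 0.80 in 20.6% (ρ = 0) or 16.4% (ρ = 0.30) of trials. The first matches the 20%.
- At the same 0.80 threshold, the chance of success if TXA halves the rate is 61.6% or 63.4%.

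**Discordant patients.** The probability of hematoma in both breasts is p11 = p1·p2 + ρ·√[p1(1−p1)p2(1−p2)]. Control-only is B = p1 − p11 and TXA-only is C = p2 − p11.

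- ρ = 0: p11 = 0.00245, B = 0.06755, C = 0.03255. Expected discordant patients: 100(B + C) = 10.0.
- ρ = 0.30: p11 = 0.00245 + 0.30 × 0.04689 = 0.01652, B = 0.05348, C = 0.01848. Expected discordant patients: 7.2.

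**Chance that the 95% interval lies below 1.** This comes from exact enumeration of the control-only and TXA-only counts:

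| Interval | ρ = 0 | ρ = 0.30 |
|---|---|---|
| Wald | 10% | 6% |
| Exact | 12% | 13% |
| Mid-P | 17% | 21% |
| Score | 18% | 24% |
| Likelihood ratio | 24% | 33% |

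The reason is visible by hand. With no TXA-only patient, the exact interval needs six control-only patients (2 × 0.5⁶ = 0.031; five give 2 × 0.5⁵ = 0.063). The expected splits are only about 6.8 to 3.3 (ρ = 0) or 5.3 to 1.8 (ρ = 0.30).

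**No finite estimate.** This happens when either discordant count is zero: (1 − C)¹⁰⁰ + (1 − B)¹⁰⁰ − (1 − B − C)¹⁰⁰.

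- ρ = 0: 0.0366 + 0.0009 − 0.00003 = 3.7%.
- ρ = 0.30: 0.1548 + 0.0041 − 0.0006 = 15.8%.

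The first term, no TXA-only hematoma, is nearly all of it.

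**Precision of the alternatives.** The medians are over trials with at least one discordant patient.

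- Exact: about 0.08 to 2.1 (ρ = 0) and 0.03 to 2.2 (ρ = 0.30).
- Mid-P: about 0.10 to 1.9 (ρ = 0) and 0.04 to 1.7 (ρ = 0.30).

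**How often the two analyses would diverge.** The share of trials with a posterior of at least 0.80 and an exact interval that includes 1 is at least the difference of the two probabilities: 61.6% − 11.5%, or 63.4% − 13.5%. That is about 50% either way, and the plan does not say how such a result is to be reported.

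**The case against.** The adequacy claim is made for the Bayesian analysis, its 80% and 20% are disclosed, and both can be reproduced. The conditional logistic regression is supplementary: nothing ties a conclusion to whether its interval excludes 1, and power was never claimed for it. The words pilot, explore and signal already appear in section 8 b). All of this stands, and it rules out several stronger readings that a reader might infer:

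- *That the sample-size calculation is wrong or its error rate hidden.* The figures reproduce and the 20% is stated openly.
- *That the trial must be enlarged.* For scale only, 80% power in a two-sided 5% paired test needs [1.96√ψ + 0.84√(ψ − d²)]²/d² patients, with ψ = B + C and d = 0.035. That gives about 459 (ρ = 0.30) to 639 (ρ = 0). The plan does not adopt that criterion.
- *That section 2, Significance, also claims adequate power.* It says "This innovative study will provide high-level evidence regarding the use of tranexamic acid in plastic surgery", and it discusses power only for earlier studies.
- *That one narrow range or a hard ceiling describes the interval's performance.* The result depends on the interval type, which the plan does not name, and on an assumed correlation. At ρ = 0.5 the likelihood-ratio figure reaches 45% while Wald falls to 3%.

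The objection leaves three things unanswered: the unqualified goal in section 3 a), the unstated precision, and an interval that fails in the trials most favourable to TXA.

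**Conclusion.** The point holds as a conflict of stated objectives and a weakness in the supplementary analysis. The goal in section 3 a) and the adequacy sentence in section 8 b) claim more than a pilot with a declared 20% false positive rate can support. At 7% versus 3.5% and an assumed outcome correlation of 0 to 0.30, the 95% interval excludes 1 in a third of trials or fewer by any of the five methods. The standard conditional estimate is not finite in about 4% to 16%.

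Two features of the plan would make this worse. Section 2 says "We have identified a hematoma rate of 7% in our patient population" without stating whether that is per patient or per breast. If it is per patient, and so about 3.5% per breast (an assumption), the Wald, exact and mid-P figures fall to about 0.2% to 7%. Section 8 a) excludes patients lost to follow-up, with no stated inflation of the sample size.

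That a wide interval will be misreported is a risk, not a certainty. It is cheap to remove before unblinding.

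**What to change.** 1. **Sections 3 a) and 8 b), objectives and sample size.** Align the goal with the pilot objective: estimate the relative risk and explore a signal. Replace the efficacy-determining goal and the adequacy sentence with the Bayesian operating characteristics, described as pilot-level. Section 2 needs no change on power.
2. **Section 8 b), interval.** Replace the standard conditional logistic (Wald) interval with one named exact or mid-P conditional interval from the discordant patients. When the TXA-only count is zero, report it as one-sided: lower limit zero, with the upper limit from the same method. A limit then exists whenever there is at least one discordant patient.
3. **Section 8 b), precision and reporting.** State the expected precision of the interval chosen in step 2, with the assumed correlation. For exact, median limits are about 0.03 to 0.08 (lower) and 2.1 to 2.2 (upper), excluding 1 in about 12% to 13% of trials. For mid-P, exclusion is in about 17% to 21%. State that an interval including 1 will not be reported as absence of effect, and that a favourable posterior will be reported as a signal.

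The cost is some protocol wording and a small change in analysis code. The stated claim becomes less favourable, and the exact interval is somewhat conservative. No extra patients are requested.

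### The prior described cannot ensure that conditional logistic regression agrees with the Bayesian relative risk, and the ordinary fit gives no finite interval in about 4% to 16% of trials under the plan's own alternative

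*Combined protocol and SAP*

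**What the plan says.** All of this is in the combined protocol and SAP, section 8, b) Statistical Analysis.

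- **Design:** "A double-blind within-subjects design will be used with each patient receiving both treatments and thus serving as their own control".
- **Prior:** each hematoma rate has a Beta(0.35, 4.65) prior with mean 0.07. On dependence: "Since patients will be treated with both treatments, the prior probabilities of developing a hematoma are not assumed to be independent", followed by "In our approach, we assume a conservative correlation of 0.30".
- **Data:** the prior is combined with "the number of observed hematomas under each treatment (a binomial random variable) to yield an estimated posterior probability distribution for each hematoma rate". The two rates then give the posterior for the relative risk (RR). The question to be answered is "what is the probability that treatment with TXA reduces the risk of hematoma, compared to control by an amount" δ.
- **Operating characteristics with 100 patients:** about 80% for estimating RR below 1 when the true RR is 0.5. Also, "the probability of observing odds of 4:1 in favor of TXA under the assumption of equal hematoma rates using each treatment is approximately 20" percent.
- **Companion analysis:** a frequentist analysis "using conditional logistic regression to estimate the odds ratio and corresponding 95% confidence interval", with the assurance that "Our use of a non-informative prior ensures that these results will be consistent with those provided by the Bayesian approach".

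**The concern.** The assurance treats the two analyses as two views of one quantity that could differ only through the prior. They estimate different quantities from different parts of the data. The Bayesian analysis, as described, uses the total number of hematomas on each treatment. Conditional logistic regression discards every patient with the same result on both sides and uses only the discordant ones.

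Two consequences follow. The odds ratio (OR) may lie further from 1 than the RR, and the fit may return no finite interval at all. Both are expected behaviour with few events, but a reader who relies on the assurance could take either as a conflict between the analyses.

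A smaller question sits beside this. The correlation is attached to the prior rates, while the data enter as one binomial count per treatment. The stated likelihood therefore does not carry the pairing.

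**Working it through.** **Inputs.** From section 8(b): n = 100, control rate pc = 0.07, TXA rate pt = 0.035 (RR 0.50), prior Beta(0.35, 4.65). Assumed: the within-patient outcome correlation ρ, taken as 0, 0.10 and 0.30 because the documents give no value; and all 100 patients analysed.

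**1. The plan's own figures.** Take independent posteriors Beta(0.35 + y, 4.65 + 100 − y) for each count y and enumerate the paired outcomes. I read the 80% as the average posterior P(RR<1) under RR 0.5, and the 20% as the chance that P(RR<1) reaches 0.8 when both rates are 7%.

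| | ρ = 0 | 0.10 | 0.30 |
|---|---|---|---|
| Mean P(RR<1) at RR 0.5, two counts | 0.789 | 0.795 | 0.809 |
| Same, paired four-cell model | 0.790 | 0.802 | 0.834 |
| Chance of 4:1 odds at equal 7% rates, two counts | 0.208 | 0.196 | 0.166 |
| Same, paired four-cell model | 0.196 | 0.197 | 0.197 |

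The paired rows use a Dirichlet prior with the plan's margins and zero prior correlation of the rates. Both models fit the stated 80% and 20% closely enough that those figures do not show which was used.

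**2. The two targets.** The probability of a hematoma on both sides is p11 = pc·pt + ρ·√[pc(1−pc)pt(1−pt)]. Control-only is C = pc − p11 and TXA-only is T = pt − p11. The conditional OR is T/C.

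| | ρ = 0 | 0.10 | 0.30 |
|---|---|---|---|
| p11 | 0.0025 | 0.0071 | 0.0165 |
| C | 0.0676 | 0.0629 | 0.0535 |
| T | 0.0326 | 0.0279 | 0.0185 |
| Conditional OR (RR is 0.50) | 0.48 | 0.44 | 0.35 |

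**3. Agreement in direction.** C − T = pc − pt, and the same identity holds for observed counts. So the OR is below 1 exactly when TXA has the lower total. The prior plays no part in this.

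**4. Empty discordant cells.** P(at least one empty) = (1−T)^100 + (1−C)^100 − (1−T−C)^100.

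- ρ = 0: 0.0365 + 0.0009 − 0.0000 = 0.037
- ρ = 0.10: 0.0593 + 0.0015 − 0.0001 = 0.061
- ρ = 0.30: 0.1548 + 0.0041 − 0.0006 = 0.158

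Nearly all of these trials have no TXA-only patient. The estimated OR is then 0 and the log OR has no finite estimate or Wald interval.

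**5. An example with fixed totals:** 7 control and 3 TXA hematomas. With two counts and independent priors, the posterior median RR is 0.43 (95% interval 0.10 to 1.48) and P(RR<1) is 0.907 in every row.

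| Patients with both sides affected | Discordant (control-only / TXA-only) | Conditional OR | Wald 95% | Exact 95% | Paired P(RR<1) |
|---|---|---|---|---|---|
| 0 | 7 / 3 | 0.43 | 0.11–1.66 | 0.07–1.88 | 0.90 |
| 1 | 6 / 2 | 0.33 | 0.07–1.65 | 0.03–1.86 | 0.93 |
| 2 | 5 / 1 | 0.20 | 0.02–1.71 | 0.004–1.79 | 0.96 |
| 3 | 4 / 0 | 0 | none | 0–1.52 | 0.99 |

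The last row is extreme: given these totals it has a chance of about 0%, 0.6% and 11% at ρ = 0, 0.10 and 0.30. With no bilateral patients, RR and OR nearly coincide.

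**6. What leaving out the pairing costs.** At equal 7% rates the two-count analysis reaches 4:1 odds in 21/20/17% of trials, so its error is conservative when ρ is positive. With false positives set to exactly 20% in both models, the signal rate at RR 0.5 is 61/64/70% with two counts and 61/63/69% paired, which is no material difference.

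**The case against.** - **The plan says consistent, not equal.** At ρ up to 0.10 the OR is 0.48 to 0.44 against an RR of 0.50, which many would call consistent. This stands as a limit on size. It does not rescue the claim that the prior guarantees it.
- **A Bayesian model of the paired data could be aimed at the conditional OR and made to agree.** True, but the section describes no such model.
- **No interval method is named.** Exact or profile methods give a finite upper limit when only the TXA-only cell is empty. This also stands: the failure belongs to the ordinary log-OR fit with a Wald interval, and the remedy is to name a method that avoids it.
- **A paired likelihood may have been used.** A reader might infer that the primary analysis ignores the pairing and is therefore wrong. The documents do not establish that. The wording describes two binomial counts, but the stated 80% and 20% are compatible with a paired model, and a paired prior could be described in the same words.
- **The 0.30 prior correlation need not be negligible.** A Gaussian-copula prior at 0.30 moves P(RR<1) at 7 versus 3 only from 0.907 to about 0.90. A prior with 30% of its mass on equal rates also has correlation 0.30 and gives 0.56. The joint prior is not stated, so its influence cannot be asserted either way.

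**Conclusion.** The assurance attributes to the prior a property that the two analyses, as described, do not have. Only the direction is guaranteed to agree. Under the plan's alternative the conditional OR is 0.48, 0.44 or 0.35 against an RR of 0.50, and an ordinary fit has no finite log OR or Wald interval in about 4%, 6% or 16% of trials. These figures rest on assumed outcome correlations of 0, 0.10 and 0.30 and on 100 analysed patients. The difference in targets does not depend on those values. The point affects the companion analysis and how it is read alongside the primary one.

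The likelihood wording is a minor, secondary matter. Pairing does not enter the likelihood as stated, and the meaning of 0.30 is left open. A reader might go further and infer a biased RR, lost control of confounding or lost power. None follows: the RR is not biased, each patient remains her own control, the error is conservative under positive correlation, and signal rates at matched error are essentially the same.

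Nor is a paired posterior shown to be the better primary analysis. Across ρ of 0 to 0.30 and equal rates of 7%, 3.5% and 2%, its 4:1 false-positive rate is 20% to 25% with the zero-correlation Dirichlet and 22% to 26% with one that keeps 0.30. The two-count analysis gives 17% to 24%.

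**What to change.** 1. **Companion analysis.** Specify exact or mid-p inference on the discordant patients. Given m discordant patients, the TXA-only count is binomial(m, θ) with θ = OR/(1+OR); transform the limits for θ to the OR scale. If one cell is empty, report the one-sided limit; if there are no discordant patients, report the OR as not estimable. The downside is somewhat conservative intervals: mid-p coverage at 7% versus 3.5% is about 95%, 97% and 98% at ρ = 0, 0.10 and 0.30.
2. **The assurance.** Replace it with a statement that the Bayesian analysis targets the marginal RR and the companion analysis a conditional OR; that only their direction is guaranteed to agree; and that they will be numerically close when few patients bleed on both sides.
3. **Clarification.** State whether 0.30 is a correlation of the two rates or of outcomes within a patient, in what sense it is conservative, the form of the joint prior, and whether the simulation used a paired likelihood.
4. **Optional sensitivity analysis.** Report a paired four-cell posterior with a pre-specified prior, giving its operating characteristics over a range of outcome correlations and base rates.

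The cost is a few lines of code and SAP text. No new data are needed, because hematoma is compared between each patient's two breasts as the primary outcome.
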